# **1.2.** Brief description of methodology, including design, population, and variables of interest

This will be a prospective randomized controlled trial of Auburn University (AU) employees or an adult sponsored dependent of an active employee (<18 years old) who was insured by the AU Health and Pharmacy Insurance plan during 2015 and enrolled in the Health Insurance plan for 2016 and/or 2017. Eligible patients are 1) those completing their "Healthy Tigers" biometric screening between 01/01/2015-5/31/16, 2) who had a BMI  $\geq$  30 and two or more of the following CVD risk factors: male, age 55-80; female, age 60-80; current smoker; family history of premature coronary heart disease; received a red or yellow zone reading for their blood pressure, blood glucose, total cholesterol; those with a diagnosis of hypertension, pre-diabetes, or hypercholsterolemia; a patient of the AU Employee Pharmacy enrolled in the TigerMeds program with an existing diagnosis of hypertension, pre-diabetes, or hypercholesterolemia. Patients will be randomized into two groups: the AHA vs MD. The study will consist of a 12-week nutrition education program that includes dietary nutrition education sessions (both groups) and extra virgin olive oil and mixed nut supplementation (MD group). We will assess program impact by comparing baseline characteristics including body mass index, blood pressure, blood glucose, and total cholesterol, etc., and reassessing the same measures at week 6 and week 12 of the study.

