#### 2. Purpose

#### 2.1. Purpose of this project including research questions and/or aims

The primary objective of this pilot study is to assess the efficacy of a MD intervention (education + EVOO and mixed nut supplementation) versus that of an AHA nutrition intervention (education) on serum blood lipid levels as markers for cardiovascular disease risk. As secondary outcomes we will assess insulin resistance, serum metabolic factors, blood pressure, body mass index, and waist circumference.

Research Question: In the Southeastern United States, is the dietary pattern of the American Heart Association or a Mediterranean style diet more effective in the reduction of CVD risk factors.

Aim 1: To assess whether or not patients have improvements in their CVD risk factors by the end of the 12-week program.

Aim 2: To assess which dietary intervention is most effective in the reduction of CVD risk factors at the end of the 12-week program.

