- c) All subjective and objective medical information collected during this appointment will be recorded in the CompuGroup Medical (CGM) electronic medical record (EMR) that is used in the Auburn University Pharmaceutical Care Center (AUPCC) and the "Healthy Tigers" programs. This EMR is a secure medical record that meets all HIPAA requirements and has been reviewed by the Harrison School of Pharmacy (HSOP) HIPAA officer, the Auburn University HIPAA officer, and the AU HIPAA consultant, and meets all legal and security requirements. These data will be perpetually stored in this EMR as required of medical data. Access to this EMR is restricted to authorized personnel only.
- 3) Baseline, 6 week and 12 week Appointments
  - a) Participants will then return to the Auburn University Pharmaceutical Care Clinic (AUPCC) for their baseline "Healthy Tigers" Healthy Hearts Program visit. Pharmacists and pharmacy residents, employed by the AUPCC will obtain the following: height measurement (inches), weight measurement (pounds), Calculated BMI (kg/m2) measurement of body composition (using bioelectrical impedance analysis) (% body fat, pounds of fat, pounds of lean mass, pounds of total body water), waist measurement (inches), hip measurement (inches), Waist to Hip Ratio, Waist to Height Ratio, Systolic blood pressure (mmHg), Diastolic blood pressure (mmHg), resting pulse (bpm), fasting blood glucose (mg/dL), fasting total cholesterol (mg/dL), fasting LDL-cholesterol (mg/dL), fasting HDL-cholesterol (mg/dL), fasting Triglycerides (mg/dL), total Cholesterol to HDL ratio, Atherosclerotic cardiovascular disease risk (ASCVD) Score (%), fasting insulin mI/L, fasting leptin ng/mL, IL-6 (pg/mL), tumor necrosis factor-α (pg/mL), plasma α linolenic acid, urinary tyrosol and hydroxytyrosol. These measurements will be repeated at week 6 and week 12 of the trial.

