- d) At the end of the baseline and 6 week appointments, participants in The Mediterranean Diet (MD) group will receive 3L of olive oil and 3 pounds of mixed nuts. Participants in the MD group will be educated by oral and written means, on consumption goals. Participants will be asked to return any unused supplements at the midpoint (week 6) and 12-week appointment. Information will be provided to the participant on how to access nutritional information used within this study and how to access the educational programming. Written instructions will also be provided.
- e) Participants will complete 3 surveys/questionnaires at their baseline visit, 6 week, and 12 week appointments. The Mediterranean diet screener and the International Physical Activity questionnaire will be completed in person. Participants will complete the web-based version of the Diet History Questionnaire II.

Participant Task		Total Involvement Time
In-Person Visits to the AUPCC	Estimated Time	
Consenting visit	45 minutes	
Baseline visit	45 minutes	
6 week visit	45 minutes	
12 week visit	45 minutes	
Total In-Person Involvement		180 Minutes
Time		
Web-Based Tasks		
Diet History Questionnaire (x3)	30 minutes each	90 minutes
Nutrition Education Modules (x7)	10 minutes each	70 minutes
Total Web-Based Involvement		160 minutes

4) Participant Involvement Time

Time	

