# **Total Participant Involvement Time**

#### 340 minutes

- 5) STUDY REQUIREMENTS
  - a) The participants will be asked to follow a dietary pattern that is associated with their assigned intervention group. The Mediterranean Diet (MD) group will be given supplements of extra virgin olive oil (EVOO) and mixed nuts. Participants in this group will be asked use these supplements as a part of their daily intake. A total of 6 L of EVOO and 6 pounds of mixed nuts (3 pounds raw walnuts and 3 pounds raw almonds) will be administered throughout the study. Participants in the MD group will be given 3 L of EVOO and 3 pounds of mixed nuts at the baseline appointment asked to return unused portions of at their 6-week appointment. At that time they will be given a new supplementation of 3 L or EVOO and 3 pounds of mixed nuts. Participants will be given the same instructions for use and asked to return unused portions at the end of the study (week 12).
  - b) The participants might have follow-up appointments scheduled with the pharmacist within the AUPCC depending on the patient's personal care plan that is developed at baseline. For instance, if a patient has potential or actual drug-related problems that are identified on their baseline MTM appointment, then the pharmacist will schedule follow-up appointments that are appropriate for the problem and the plan of care that is developed to address these problems. This will be done consistently between all patients in the study, regardless of the randomization (the pharmacist and the will be blinded concerning which group the patient is randomized to concerning dietary intervention).
  - c) Narrated nutrition education presentations will be developed by a registered dietitians, dietetic interns, graduate students, and faculty. These presentations will be loaded on the "Healthy Hearts Program" website. The participants will be asked one presentation weekly for the first 6 weeks of the study and then one additional education module at week 9. A post-presentation assessments will load after the presentation is completed, and completion of the assessment will be used as verification that the participant watched the presentation.
  - d) The participant will complete the following at baseline, week-6 and week 12 of the study: Diet History Questionnaire II, International Physical Activity Questionnaire, and a Mediterranean diet knowledge and adherence questionnaire.

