#### 4.5. Data analysis

Descriptive statistics will be conducted and presented for the population. Baseline demographics will be compared between the 2 groups and compared using the appropriate test for each data point. Continuous variables will be compared using student t-tests, categorical variables will be compared using chi-square tests, etc. Age will be collected as a continuous variable (years). Ethnicity will be collected as a categorical variable (Caucasian, Asian, African-American, Hispanic, Other, Not Reported). Level of education will be collected as a categorical variable (high school, some college, college degree, graduate degree, professional degree, etc.), smoking status will be collected as a categorical variable (never smoked, past smoker, current smoker), baseline ASCVD risk score (collected as a continuous variable), obesity (dichotomous), HTN (dichotomous), hypercholesterolemia (dichotomous), Number of patients with 1 disease state (continuous), number of patients with 2 disease states (continuous), number of patients with 4 disease states (continuous), number of yellow values (continuous), number of red zone values (continuous).

Baseline data on change in baseline body weight (%), change in total body weight (kg), calculated BMI (kg/m2) measurement of body composition (using bioelectrical impedance analysis) (% body fat, pounds of fat, pounds of lean mass, pounds of total body water), waist measurement (inches), hip measurement (inches), Waist to Hip Ratio, Waist to Height Ratio, Systolic blood pressure (mmHg), Diastolic blood pressure (mmHg), resting pulse (bpm), fasting blood glucose (mg/dL), fasting total cholesterol (mg/dL), fasting LDL-cholesterol (mg/dL), fasting HDL-cholesterol (mg/dL), fasting Triglycerides (mg/dL), total Cholesterol to HDL ratio, and ASCVD Score (%)) fasting insulin mI/L, fasting leptin ng/mL, IL-6 (pg/mL), tumor necrosis factor-α (pg/mL), urinary tyrosol and hydroxytyrosol, will be compared to data at week-6 and the end of the 12 weeks

- Student's T test will be used to compare the continuous data collected in the study
- Chi Square test will be used to compare the categorical data collected in the study

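### The only method for lipid outcomes is a t-test with no analysis set or missing-data rule, so the week 12 MD-versus-AHA comparison omits everyone without a week 12 value and can be biased if dropout is both unequal and lipid-related

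*Combined protocol and SAP*

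**What the plan says.** - **Question.** Section 2.1 sets the primary objective as MD against AHA "on serum blood lipid levels as markers for cardiovascular disease risk". Aim 2 asks which diet does better at the end of the 12 weeks. No single lipid is named as primary.
- **Design.** Section 1.2: "Patients will be randomized into two groups: the AHA vs MD".
- **Measurement.** Section 4.2 lists the lipid panel at baseline and adds "These measurements will be repeated at week 6 and week 12 of the trial". This applies to both arms.
- **Analysis.** Section 4.5 says that baseline data "will be compared to data at week-6 and the end of the 12 weeks", and that "Student's T test will be used to compare the continuous data collected in the study". It does not say whether the tests are paired or between arms, who is analysed, or what happens to missing values.
- **Supplies.** Section 4.2, item 3 d): "At the end of the baseline and 6 week appointments, participants in The Mediterranean Diet (MD) group will receive 3L of olive oil", together with mixed nuts. Item 5 a) repeats this for week 6: "At that time they will be given a new supplementation of 3 L or EVOO and 3 pounds of mixed nuts". At week 12 these participants are only "asked to return unused portions at the end of the study (week 12").
- **Follow-up.** Section 4.2, item 5 g) asks all participants to come back at weeks 6 and 12. Section 4.3 excuses a participant from the blood draw after three failed attempts. The data form in section 4.4 has no field for the date of, or reason for, stopping.

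**The concern.** A t-test on week 12 values, or on change to week 12, can use only people who have a week 12 value. People who miss the visit, or whose blood cannot be drawn, drop out of the contrast that answers Aim 2. Their earlier lipids then play no part in it.

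This matters if the missing people differ between arms. One arm is given food at two visits and the other is not, and participants know which they are in, so unequal retention is plausible. Suppose participants who are not improving leave more often, and more people leave the AHA arm. The remaining AHA group then looks better than the group that was randomised, and the contrast shifts against MD. Because the plan sets no rule, the handling of these people would be decided after the data are seen.

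**Working it through.** The documents state no sample size, SD, effect or dropout rate, so there is no planned figure to reproduce. LDL serves as an example, and every input below is an assumption.

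**Inputs.** SD 30 mg/dL at each visit. Correlations: baseline with week 6 0.75, baseline with week 12 0.70, week 6 with week 12 0.75. Same true mean change in both arms, so the true MD minus AHA difference is 0. Dropout after week 6 is 10% in MD and 20% or 30% in AHA. The log-odds of dropout rise by b = 0.5 or 1.0 per SD of worse week 6 change, with the same b in both arms.

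**Step 1: link between week 6 change and week 12 change.**
- SD of week 6 change = 30 × √(2 × 0.25) = 21.2.
- Covariance of the two changes = 900 × (0.75 − 0.70 − 0.75 + 1) = 270.
- Expected week 12 change per SD of week 6 change = 270 / 21.2 = 12.73 mg/dL.

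**Step 2: bias among completers.** With dropout proportion d and mean standardised week 6 change e among those who drop out, the completers' mean change is too low by 12.73 × e × d/(1 − d). The bias in MD minus AHA is the AHA term minus the MD term. The values of e come from numerical integration of the logistic dropout curve over a standard normal.

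| b | e at d = 10%, 20%, 30% | Bias, 10% vs 20% | Bias, 10% vs 30% |
|---|---|---|---|
| 0.5 | 0.440, 0.385, 0.333 | 12.73 × (0.25 × 0.385 − 0.111 × 0.440) = 0.6 | 12.73 × (0.429 × 0.333 − 0.111 × 0.440) = 1.2 |
| 1.0 | 0.817, 0.693, 0.590 | 12.73 × (0.25 × 0.693 − 0.111 × 0.817) = 1.0 | 12.73 × (0.429 × 0.590 − 0.111 × 0.817) = 2.1 |

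Positive values run against MD. Simulation with 1,000,000 per arm gives the same range.

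**Step 3: when there is no bias.** With equal dropout and the same b, the two terms cancel. With b = 0, e = 0. Simulations of both cases (10/10, 20/20, and unrelated dropout at 10/30) gave values within 0.1 of 0.

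**Step 4: what the earlier visits recover.** Missing week 12 values were predicted by regression on the available baseline and week 6 values, as a stand-in for a mixed model under missing at random. These runs used equal correlations of 0.6 or 0.8, b = 1, and dropout of 10% against 20 to 30%.

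| Pattern of loss | Completer bias (mg/dL) | Bias left (mg/dL) |
|---|---|---|
| All after an attended week 6 visit, driven by week 6 change | 0.8 to 2.2 | within 0.1 of 0 |
| Half lost before week 6 | 0.8 to 2.2 | 0.2 to 0.5 |
| All lost before week 6 | 0.8 to 2.2 | 0.6 to 1.3 |
| Driven by the unseen week 12 change | 1.5 to 4.2 | 1.1 to 3.1 |

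With the step 1 correlations and b of 0.5 to 1.0, the last row leaves about 0.7 to 2.7.

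**Step 5: effect on the test.** SD of week 12 change = 30 × √(2 × 0.30) = 23.2. With an assumed 50 per arm and dropout of 10% and 30%, SE = 23.2 × √(1/45 + 1/35) = 5.24. A 2 mg/dL bias is 0.38 SE, so two-sided type I error is Φ(0.38 − 1.96) + Φ(−0.38 − 1.96) ≈ 0.067. With 20 per arm it is 0.057.

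**The case against.** The trial team can say that four stronger readings go beyond the text. On these the team is right.

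- A reader might infer that the plan restricts analysis to week 12 attenders. No section says so. Week 6 comparisons are also planned and would include people who leave later. The omission follows from the named test and the plan's silence.
- A reader might infer that the food rewards week 12 attendance. It is handed out at baseline and week 6, and nothing is given at week 12, so the link to week 12 is indirect. Both arms also receive repeat screening, medication consultations, education and dietitian access, and no figure shows that retention differs.
- A reader might infer that nothing keeps someone who stops the diet in follow-up. Section 4.2, item 5 g) asks everyone to return, without an adherence condition, and no section ends participation for stopping. Section 3.1 also excludes people who expect to be absent or cannot travel to campus, although this does not cover later dropout.
- A reader might infer that week 6 lipids would correct the bias. They do so only for people who attended week 6 and whose later loss depends on what was observed. The food acts on week 6 attendance, so the people it fails to hold may have no week 6 lipids at all.

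The team can add that the size is assumed throughout and modest, and that this is a pilot. That is also fair. What remains is that the only named method discards collected data from randomised participants in the comparison the trial is built on, and that no rule covers missing values.

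**Conclusion.** The point stands in a limited form. Section 4.5 gives a t-test without an analysis set or missing-data method, so the week 12 contrast omits anyone without a week 12 lipid value. Bias arises only if dropout differs by arm and is related to lipids. Then it is about 0.6 to 2.1 mg/dL LDL under the step 1 and 2 assumptions; otherwise it is about 0. A 2 mg/dL bias would move type I error from 5% to about 6 to 7% with an assumed 20 to 50 per arm. The documents show neither that such dropout will occur nor its direction. The change is worth making because the data are already to be collected and the better method is routine. It is an improvement to the plan and does not show that the result will be wrong.

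**What to change.** 1. **Section 4.5, analysis.** Make the between-arm lipid comparison a mixed model for repeated measures at baseline, week 6 and week 12, with arm-by-visit terms. Include all randomised participants in their assigned arm. The week 12 arm difference is the result; state whether it is in level or in change from baseline. Keep the t-test as supportive.
2. **Section 4.5, reporting.** Give week 6 and week 12 attendance by arm, counting attenders without a blood sample separately.
3. **Section 4.5, sensitivity.** Add a simple analysis for data not missing at random, such as shifting the predicted week 12 lipids of those missing by a range of amounts, separately by arm.
4. **Section 4.2, item 5 g).** Clarify that the request to return at weeks 6 and 12 also covers participants who stop the diet, supplements or modules. A stop date and reason on the section 4.4 form would help interpret the losses.

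**Cost.** Some wording, two form fields and a standard model; no new measurements for those who attend as planned. The model assumes missing at random. It reduces, but does not remove, bias from losses before week 6 or losses that depend on unseen values, which is why items 3 and 4 belong with it. Including people who stopped may also make the observed effect smaller.

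### Section 4.5 uses an unadjusted Student's t test for every continuous variable; if triglycerides and several biomarkers are right-skewed with proportional effects, this costs power that a baseline-adjusted log-scale analysis would keep

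*Combined protocol and SAP*

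**What the plan says.** Section 4.5 states the method for continuous outcomes in one line: "Student's T test will be used to compare the continuous data collected in the study". The variables it covers include "fasting Triglycerides (mg/dL") and "fasting insulin mI/L, fasting leptin ng/mL, IL-6 (pg/mL), tumor necrosis factor-α (pg/mL), urinary tyrosol and hydroxytyrosol". Where units are given they are ordinary measurement units. No section mentions a transformation, a check of distribution, a rank-based alternative or adjustment for baseline.

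The contrast is described only as baseline data that "will be compared to data at week-6 and the end of the 12 weeks". The plan does not say whether the t test is paired within an arm, compares the arms on follow-up values, or compares them on change.

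Section 2.1 sets the primary objective as the effect of the Mediterranean programme against the AHA programme "on serum blood lipid levels as markers for cardiovascular disease risk". No single lipid is named, so triglycerides are one of several lipids under that objective. The comparative aim is Aim 2: "To assess which dietary intervention is most effective in the reduction of CVD risk factors at the end of the 12-week program". Section 1.2 confirms the randomised comparison: "Patients will be randomized into two groups: the AHA vs MD".

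The documents give no sample size, alpha, power, effect size, SD, skewness or baseline-to-follow-up correlation.

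**The concern.** Triglycerides, insulin, leptin, the two cytokines and the urinary phenols are positive concentrations. Measures of this kind can have a long right tail, with treatment effects closer to a percentage change than to a fixed number of units. If so, a few high values inflate the raw-scale SD, and the raw t test is less sensitive than the same comparison on the log scale. Each participant's baseline value is collected but, apart from the unspecified comparison with baseline, has no stated role in the between-arm comparison. That gives up precision on either scale.

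At stake is sensitivity. A study that calls itself a pilot yet has an efficacy objective could miss a real difference in one of its primary lipids, or in insulin and the other biomarkers, that the same data could have shown.

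**Working it through.** **Inputs.** The documents supply the test, the list of variables, the two arms and the visits at baseline, week 6 and week 12. They state no power figure to reproduce. Everything else is assumed: 30 per arm with equal allocation, two-sided 0.05, log-normal values, a constant treatment ratio, no dropout, and correlation ρ of 0.6 to 0.7 between log baseline and log week 12. Three levels of skew are shown: log SD (σ) 0.45 with ratio 0.80, 0.60 with 0.75, and 0.80 with 0.70.

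**Step 1: large-sample efficiency on follow-up values.** For a log-normal outcome and a small proportional effect, the efficiency of the raw t test relative to the log t test is σ²/(exp(σ²) − 1):
- σ = 0.45: 0.2025/0.2245 = 0.90
- σ = 0.60: 0.36/0.4333 = 0.83
- σ = 0.80: 0.64/0.8965 = 0.71

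The loss is modest at the low end and grows with skew.

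**Step 2: log-scale power by formula.** The standard error is σ·k·√(2/n), where k = 1 for follow-up values, √(2(1 − ρ)) for change and √(1 − ρ²) for ANCOVA. For σ = 0.45, ratio 0.80, ρ = 0.6 and n = 30, the effect is |ln 0.80| = 0.2231 and √(2/30) = 0.2582.
- Follow-up: SE 0.1162; 0.2231/0.1162 = 1.92; power 0.472
- Change: SE 0.1039; ratio 2.15; power 0.560
- ANCOVA: SE 0.0930; ratio 2.40; power 0.655

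Powers are from the noncentral t distribution. They agree with the simulated log-scale values at ρ = 0.6 in step 3 to within about two points.

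**Step 3: simulated power, raw against log.** Ranges run over ρ = 0.6 to 0.7. The change and ANCOVA columns use 6,000 simulated trials per setting.

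| σ, ratio | Week-12 t test | Change t test | ANCOVA |
|---|---|---|---|
| 0.45, 0.80 | 0.43–0.44 v 0.47–0.48 | 0.45–0.56 v 0.55–0.68 | 0.58–0.69 v 0.64–0.75 |
| 0.60, 0.75 | 0.38–0.40 v 0.44–0.46 | 0.38–0.48 v 0.54–0.66 | 0.53–0.62 v 0.63–0.72 |
| 0.80, 0.70 | 0.31–0.32 v 0.39–0.40 | 0.28–0.35 v 0.47–0.59 | 0.40–0.49 v 0.55–0.65 |

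Repeat runs differ by a point or two. Across runs, the log scale alone gains about 4 to 9 points on week-12 values, 11 to 24 on change and 5 to 17 under ANCOVA. Log-scale ANCOVA against a raw t test, on follow-up or change, gains about 17 to 35 points.

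**Step 4: where the gain comes from.** At σ = 0.45, moving from the raw week-12 t test to raw ANCOVA takes power from about 0.44 to 0.58–0.69, a gain of 14 to 25 points. Logging then adds about 6. At σ = 0.80, adjustment takes it from about 0.32 to 0.40–0.49, a gain of 8 to 17 points, and logging adds 15 to 16. For mild skew, baseline adjustment does most of the work. For strong skew, the two contribute comparably.

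**Step 5: type I error.** Under no effect, at 25 per arm and log SD 0.5 or 1.0, the raw t tests rejected in about 0.035 to 0.049 of trials. The nominal level is kept.

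**Step 6: a different form of effect.** Suppose only about the top third by baseline respond, with ratio 0.6 among them, σ = 0.45 and ρ = 0.65. Raw against log power is then 0.41 v 0.36 on follow-up, 0.33 v 0.32 on change and 0.47 v 0.43 under ANCOVA. At σ = 0.80 the raw scale still leads on follow-up and ANCOVA, while on change the log scale is slightly ahead (0.31 v 0.28 raw). The log scale's advantage depends on the effect being roughly proportional.

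**The case against.** The strongest objection is to size. A reader might infer that the planned test loses a large part of its power. The documents do not support that: sample size, skew, correlation and the proportional effect are all assumed. The larger losses also need a comparison of raw change scores, which the plan never specifies. On week-12 values the log scale alone is worth only 4 to 9 points. For triglyceride-like skew, baseline adjustment matters more than the choice of scale. All of this stands, and the point is sized accordingly.

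A reader might also infer that the t test is invalid here. It is not: type I error is held, and a difference in arithmetic means in mg/dL is a legitimate quantity. A log analysis answers a slightly different question.

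Third, raw-scale analysis is inferred from silence and the listed units; the plan does not exclude a transformation. That is fair. But an unstated transformation leaves the scale open to choice after the data are seen, which is itself a reason to specify it.

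Finally, section 2.1 names no individual lipid, and its secondary outcomes do not name leptin, IL-6, TNF-alpha or the urinary phenols. Triglycerides are fairly read as part of the primary objective, but not as its sole endpoint, and the biomarkers should not be called named secondary outcomes.

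None of this removes the core. The plan states one method for very different variables, and a better one is available from data already collected.

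**Conclusion.** The point holds in a limited form. Section 4.5 prescribes an unadjusted t test for every continuous variable, including several that may well be right-skewed. If they are, and effects are roughly proportional, the test has less power than baseline-adjusted analysis on the log scale. Under the stated assumptions the full change is worth about 17 to 35 points of power, much of it from baseline adjustment. The part due to the log scale alone is small to material, depending on skew and contrast. False-positive risk is unaffected, and the advantage of the log scale shrinks or can reverse if effects are not proportional. This is an improvement worth making before the data are analysed, not a flaw that invalidates the comparison.

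**What to change.** In section 4.5, replace the single t-test rule for the between-arm comparison with the following:
- State the contrast: compare the arms at week 12, and also at week 6, by ANCOVA adjusted for the participant's baseline value of the same variable.
- Pre-specify natural-log transformation of both outcome and baseline for triglycerides, insulin, leptin, IL-6, TNF-alpha, tyrosol and hydroxytyrosol. Report ratios of geometric means with 95% CIs.
- Keep the raw scale for roughly symmetric measures: total, LDL and HDL cholesterol, blood pressure and anthropometry.

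The cost is wording only, with no new visits, samples or participants. The downside is that effects for the logged variables are reported as ratios rather than unit differences; arm summaries in original units can still be tabulated alongside. The plan should also say how a value below an assay's limit is handled, since zero cannot be logged.
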